2. What are the sociodemographic and clinical characteristics of patients that may influence results regarding measurement of clinical and organizational quality indicators of acute stroke care?

Research hypotheses

1. Results highlight gaps between guidelines and practice following measurement of clinical and organizational quality indicators during acute management of patients with ischemic stroke.
2. Gaps between guidelines and practice resulting from measurement of the clinical and organizational quality indicators of acute stroke care may present similarities or differences between types of hospital centers.
3. Some of patients' clinical and sociodemographic characteristics influence the achievement of the clinical and organizational quality indicators of acute stroke care.
4. Patients' sociodemographic and clinical characteristics identified as influencing the achievement of clinical and organizational quality indicators may vary depending on types of centers.

3. Methodology

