3.3.2 Sample size

Calculation of number of records aims for a certain representativity of the target population at the time of data collection. Given that about 660 patients are hospitalized each year with ischemic stroke in the three centers under study - 400 in the tertiary center, 250 in the secondary center and 12 in the primary center - and the data were collected over a period of 6 months, the sample size is estimated to be some 130 health records, i.e., about 75, 45 and 8 to 10 records respectively. A power calculation in G*Power on analyses of group averages indicates this sample size is largely sufficient to have a power of 95 %, an alpha set at 0.05 and a minimal size effect of 0.5. When the size effect is not known, a minimal size effect of 50 % is acceptable (Julien, 2019). However, a first phase test will be performed with the health records of patients (n =6) hospitalized prior to the date set for the start of data collection to evaluate the average time required to analyze a record. This phase test will be performed on three health records from the secondary center and three from the tertiary center. Finally, this phase will enable needed adjustments to be made regarding implementation of research within the context of a doctoral study. Additionally, the principal investigator will have access to resources to validate the statistical analysis plan for the study duration.

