3.5 Projected statistical analyses

In response to the first research question, descriptive analyses will be conducted based on measurement of the clinical and organizational quality indicators identified in the acute phase. Medians and interquartile ranges, means and standard deviations and proportions will be used to describe performance of care and services for each center under study and comprehensively for all three centers. Additionally, a contextual description of each center will be presented using data collected on the hospitals' characteristics.

Results of the first objective will highlight indicators that do or do not meet the guidelines for quality of care for persons with ischemic stroke and their caregivers. For indicators presenting extensive data, regression analyses will be performed to identify the determinants likely to influence results regarding these indicators.

Dependent variables are clinical or organizational quality indicators, while independent variables correspond to the sociodemographic characteristics and clinical profile of patients with ischemic stroke. Type of regression analysis will vary consistent with the nature of the dependent variables (dichotomous or continuous) and their distribution (parametric or nonparametric tests).

A univariate regression analysis will first allow us to associate determinants (independent variables) with results for the indicators (dependent variables). Variables with a statistically significant association will then be introduced into a linear or logistic regression model. Additionally, these regression analyses will include

confounding variables that may also influence results from the measurement of clinical and organizational quality indicators. To be statistically significant, results must obtain a value of $p < 0.05$ and have a confidence interval of 95 %. All statistical analyses will be conducted using SPSS 28.0 software. Results will be presented comprehensively for the three centers; they may also be presented individually for the secondary and tertiary centers to see if the associations in them are similar or different. If the number of records in one of these hospitals is not enough for statistical power, the analysis will not be performed.

4. Consent process

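### Hypothesis 4 asks whether associations differ between types of centre, but section 3.5 only offers optional separate results for two hospitals and never estimates the difference

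*Protocol*

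**What the plan says.** Research hypothesis 4 in section 2 of the protocol reads: "Patients' sociodemographic and clinical characteristics identified as influencing the achievement of clinical and organizational quality indicators may vary depending on types of centers".

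Section 3.5 presents the regression results for the three centres together. On differences between centres it adds only that "they may also be presented individually for the secondary and tertiary centers to see if the associations in them are similar or different". It then limits this: "If the number of records in one of these hospitals is not enough for statistical power, the analysis will not be performed". No number of records or level of power is attached to that condition. The primary centre is not part of the by-centre presentation.

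The only criterion for judging results in section 3.5 begins "To be statistically significant, results must obtain a value of" p < 0.05, with a 95% confidence interval. Univariate significance also decides which characteristics enter the models: "Variables with a statistically significant association will then be introduced into a linear or logistic regression model". In addition, the models are to include "confounding variables that may also influence results from the measurement of clinical and organizational quality indicators".

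Section 3.3.2 expects "about 75, 45 and 8 to 10 records respectively" from the tertiary, secondary and primary centres, and states "a power of 95 %, an alpha set at 0.05 and a minimal size effect of 0.5" for a comparison of group averages. It does not say whether 0.5 is a standardised mean difference (Cohen's d) or Cohen's f.

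**The concern.** Hypothesis 4 is about a difference between associations. Two sets of results placed next to each other do not estimate that difference, and they give no measure of its uncertainty. The two samples are of unequal size, so they have unequal power. The same true association can reach significance at the tertiary hospital and miss it at the secondary one, and could then be reported as a determinant that varies by type of centre. If the univariate screen is repeated within each hospital, the two final models may also hold different covariates, so their coefficients would not be comparable.

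The condition for dropping the separate analyses adds a second problem. Depending on the threshold applied, hypothesis 4 gets either a side-by-side reading or nothing.

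**Working it through.** **Inputs from the protocol.** Tertiary 75 and secondary 45 records, two-group alpha 0.05, planned effect 0.5 and power 95% (sections 3.3.2 and 3.5). **Assumed, because the protocol gives no figures:** two-sided tests, a binary characteristic that splits each hospital's records equally, and an indicator measured in SD units.

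**1. The protocol's own power statement.** For a three-group analysis of variance with f = 0.5, 95% power needs 66 records, and 130 records give over 99.9%. The claim that the sample is largely sufficient reproduces on this reading. For a two-group comparison with d = 0.5, 65 against 65 gives 81% and 75 against 45 gives 75%, so on that reading it does not. Both readings are therefore carried forward. With two equal groups, f = 0.5 corresponds to d = 1.0.

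**2. Same true association in both hospitals, each tested separately.** Power is from the noncentral t distribution with n/2 records per group. The chance that exactly one hospital is significant is P_T(1 − P_S) + P_S(1 − P_T).

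| True effect (both hospitals) | Power, tertiary (75) | Power, secondary (45) | Exactly one significant |
|---|---|---|---|
| 0.3 SD | 25% | 17% | 33% |
| 0.5 SD | 57% | 37% | 52% |
| 0.8 SD | 93% | 75% | 29% |
| 1.0 SD | 99% | 91% | 10% |

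For 0.5 SD: 0.570 × 0.625 + 0.375 × 0.430 = 0.356 + 0.161 = 0.52.

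Many indicators are proportions. For a binary indicator (assumed 50% exposure and about 50% achievement, 10,000 simulations) with the same odds ratio of 2, 3 or 4 in both hospitals, exactly one is significant in 38%, 52% and 42% of studies. A test of the interaction rejects in about 5%, as it should.

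**3. The dropping rule at the 95% power target.** If 0.5 is d, 95% power needs 210 records in a hospital; the two have 57% and 37%, so neither qualifies. If 0.5 is f, 95% power needs 54 records; the tertiary hospital qualifies (99%) and the secondary does not (91%). On both readings the secondary hospital fails, so the comparison would be cancelled.

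**4. What a direct estimate would give.** For a 50:50 characteristic the variance of the association in a hospital with n records is 4/n, in squared SD units. The standard error of the difference is √(4/75 + 4/45) = √(0.0533 + 0.0889) = 0.377 SD.

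- 95% CI half-width: 1.96 × 0.377 = 0.74 SD.
- Power (normal approximation): 26% for a difference of 0.5 SD and 56% for 0.8 SD.
- Difference detectable with 80% power: 2.80 × 0.377 = 1.06 SD.
- At 30% prevalence instead of 50%, the half-width is 0.81 SD and power for 0.5 SD is 23%.

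**The case against.** Four objections carry weight.

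- **The comparison rule is not stated.** Section 3.5 does not say that centres will be compared by which of them reaches p < 0.05; that sentence defines when a result is significant. If readers instead looked for non-overlapping 95% intervals, false differences would be rare (about 0.6% in the binary simulation). This stands, so the percentages in the table are conditional. Non-overlap is a poor substitute, however: for a true ratio of odds ratios of 4 it has 18% power, against 45% for the interaction test.
- **The dropping rule may prevent the false contrast.** Applied at 95% power, it removes the separate analyses, and the 52% figure could not arise. This also stands. The two harms are alternatives: a misleading contrast under a lax threshold, or no analysis under a strict one.
- **This is detail for a statistical analysis plan.** Only in part. The protocol does not leave the method open; it names one and gives its purpose, and that method does not estimate what the hypothesis asks.
- **The stakes are low and the remedy is weak.** Hypothesis 4 says only that characteristics may vary, the study is descriptive-correlational, and an interaction estimate from 120 records is imprecise. This limits the weight of the point. It does not favour reading the two hospitals side by side, because that reading hides the imprecision that an interval would show.

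A reader might also infer that centre has to be forced into the pooled models. The text does not support that request: section 3.5 already adds confounders besides the screened variables. In simulation with strong centre differences (a null characteristic present in 40% against 5%, achievement 80% against 50%), keeping centre always rather than screening it changes the false-positive rate only from 2.0% to 1.7%.

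**Conclusion.** The point holds as a minor one. Section 3.5 gives hypothesis 4 a method that neither estimates nor tests the difference between centres, and it makes even that method optional and removable under an undefined power condition.

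If the separate results are produced and read by significance, an identical association would look different between the two hospitals in about 10% to 52% of studies over true effects of 0.3 to 1.0 SD. This rests on equal groups and two-sided tests.

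Two stronger readings should not be drawn. The first is that 52% is the error rate at the protocol's planned effect. That holds only if 0.5 means d; if it means f, the figure is about 10%. The second is that neither hospital has enough records at the planning values. That too holds only for d. What holds on both readings is that the secondary hospital misses 95% power (37% or 91%), so enforcing that target would leave hypothesis 4 without any analysis.

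**What to change.** In section 3.5:

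1. Assess hypothesis 4 with a centre-by-characteristic term, including both main effects and the same covariates for both hospitals, fitted to the tertiary and secondary records together.
2. Report it as an exploratory difference in association with its 95% CI.
3. Keep the hospital-specific results as description, not as the means of comparison.
4. State that precision is low (about ±0.74 SD, and 26% power for a 0.5 SD difference, under the assumptions above), that a non-significant interaction does not show similarity, and that the contrast is between two hospitals rather than between types of centre.

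The cost is a few sentences. Centre and the patient characteristics are already on the collection sheet in Appendix 2, and no further records are needed. The models lose one or more degrees of freedom per interaction, and the resulting estimate will be imprecise.

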6.1 Tri-Council Policy Statement (TCPS2)

As defined, this protocol is intended to confirm that the principal investigator respects the principles of the Tri-Council Policy Statement ensuring the security and confidentiality of the data collected in patients' health records.

6.2 Ethics review

This research protocol and the documents in the appendices will be evaluated and approved by the Research Ethics Board. A convenience evaluation must be obtained and conducted for each center included in the multicentric study. The ethics certificate must be issued before the project is started. Additionally, this protocol must be evaluated and approved by the ethics committee of the UQTR, the university hosting the principal investigator, whose project will be implemented within the context of her doctoral studies.

6.3 Confidentiality

Every effort will be made to ensure the anonymity of patient health records included in the research. None of the records will be photocopied, and data will be collected in an area designated for this purpose in each of the three centers. Records will be assigned a digital identification code in a password-secured file stored separately from the collected data. It will be possible to trace the identity of patients, but only the principal investigator and her research assistant can access the records. At no time will the names of patients in the records be divulged. The data extraction grid needed to perform statistical analyses will contain no identifiable information allowing patients to be traced. Data collection sheets will be stored in a locked filing cabinet in Local G2 110D located in the Centre hospitalier affilié universitaire régional (CHAUR) de Trois-Rivières. The data will be entered into a database in a password-protected Excel file on the password-protected research computer belonging to the principal investigator. No document identifying the participants will leave the investigational site.

6.4 User data retention and archiving

All documents associated with this project will be kept by the principal investigator. Electronic data will be deposited in a UQTR institutional data repository server, Borealis (Dataverse), which is available to institutions and research organizations in Canada only. Borealis ensures the long-term retention of data, access to the data, and the attribution of unique and permanent digital object identifiers (DOI). Two types of data will be deposited in this server: raw data (untreated data drawn directly from patients' records) and treated data (raw data manipulated in preparation for transfer to SPSS for statistical analyses). Data are anonymous and contain no direct identifiers. Additionally, the hospital centers under study will be identified as primary, secondary or tertiary in the data dictionary accompanying the databases. To facilitate interoperability, data will be saved in an open-access Excel file (CSV). Data can be accessed by contacting the principal investigator. To ensure continuity of access, a second person may be charged with managing data deposit and granting access to data upon request.

6.5 Benefits

Anticipated benefits include contribution to the advancement of knowledge aimed at improving the acute care management of adults with ischemic stroke and their caregivers.

6.6 Risks for patients

There are no concerns regarding risks to patients. Every effort will be made to protect patients' privacy and the confidentiality of the results obtained. The file containing records' identifying numbers will be kept separate from the data collection file, thus ensuring that patients cannot be identified.

7. Source of funding

Previous or pending grants

A grant from the Fonds de soutien à la recherche de la Fondation régionale de Trois-Rivières (RSTR) in the amount of \$12,000 was obtained in May 2021. This sum covered a portion of the expenses incurred during the scoping review prior to conducting this study and will allow us to engage a research assistant to help with data collection.

The following internship grants and scholarships were also obtained.

- 1) Scholarship from Tremplin-Fonds de recherche du Québec-Santé (FRQS) to perform an internship at the Institut national d'excellence en santé et services sociaux (INESSS). Obtained in 2021/05.
- 2) Scholarship from MES-Universités-Bourses d'études doctorales-Concours 2020-2021. Obtained in 2020/09 and 2021/09.
- 3) Scholarship from university partners of the Réseau de recherche en interventions en sciences infirmières du Québec (RRISIQ). Obtained in 2020/10 and 2021/10.

8. Impacts of this research project

First, this research project will help broaden the state of knowledge regarding acute ischemic stroke by describing how these patients are managed in three differently-designated Quebec hospitals. Additionally, the results will allow for a clinical and organizational look at performance of care and services by highlighting concepts with the highest-performing results regarding measurement of indicators or, conversely, the lowest-performing. Indeed, this study is the first that measures quality indicators for acute stroke based on dimensions of performance of care in order to shed light on clinical and organizational practices relating to accessibility of services (accessibility and equity of access), optimization of resources (efficiency and viability) and quality of care (safety, effectiveness, continuity and reactivity). Furthermore, the results of measuring clinical and organizational quality indicators will highlight indicators calling for improvement and those for which variations have been observed.

Second, the project will also identify the sociodemographic and clinical determinants potentially able to influence the results of certain indicators. This new knowledge will greatly help strengthen our understanding of the possible impact of certain determinants on patient management and would favor the development of an interdisciplinary intervention model better adapted to the needs of patients and caregivers in terms of improved physical, psychological and cognitive post-stroke recovery.

In the long term, this project may help reduce the gap between current practices and guidelines regarding post-stroke patient management. Finally, because it is conducted in different types of Quebec hospital centers, this project will enable a better understanding of various contexts that is conducive to the optimization of acute stroke care and services across Quebec. Based on the project's results, strategies of improvement through innovative interdisciplinary interventions could be developed that favor optimal management adapted to stroke patients' needs.

8.1 Strengths

This first study on the measurement of acute stroke quality indicators in Quebec allows for an evaluation of performance of care and services based on various clinical and organizational aspects. Indeed, the study's main strength is the measurement of diverse dimensions of performance of care that enables a picture of interdisciplinary practice for the entire acute phase of ischemic stroke. The implementation of the study in three different Quebec hospitals will also provide a better understanding of their distinct geographic and structural contexts. Inclusion of health records from three different centers also allows for better representativity of the population with stroke. As well, the rigorous method employed during implementation can be used by other organizations to obtain results specific to their own establishment. Finally, this retrospective study including a data collection close in time will enable an accurate picture of clinical and organizational management within the context of current healthcare.

8.2 Limitations

The study's main limitation involves the level of data collection in the health records of different hospitals whose different and separate databases complicate the research. Additionally, retrospective research has certain limitations including the possibility of missing data during measurement of indicators or data that vary depending on the quality of notes in the records, factors the researcher cannot control for. What's more, input errors may occur during data collection. To limit this type of error during data collection in health records, an automated coding system will be inserted in the file with a drop-down menu to enter textual data. A validation system will be integrated to issue an error message if aberrant data are recorded. As well, a data validation will be regularly performed to ensure the quality of the data collected by the research assistant. Although the number of indicators to measure ensures good representativity of acute patient management, priority indicators must be chosen to make data collection feasible within the context of a doctoral study. Additionally, certain hospital characteristics must be collected through observation and consultations with various available on-site stakeholders given the lack of written documentation on the subject in the different centers. Finally, the association between

determinants and results will not explain the cause of the different results, but will further identify the elements likely to influence the results obtained.

Numerator: Total number of remote communities served by the center and having access to the Telehealth/Telestroke program which facilitates access to organized stroke care across the continuum of care, notably evaluation of needs and delivery of care related to post-stroke rehabilitation

Denominator: Total number of remote communities that could treat ischemic stroke

Indicator 6

Percentage increase of the Telehealth/Telestroke program's coverage of remote communities to support organized stroke care across the continuum of care

Optimization of resources

Efficiency

Indicator 7

Proportion of hospitalized patients treated in a stroke care unit (Not applicable in a primary care center)

Numerator: Number of hospitalized patients treated in a stroke care unit

Denominator: Total number of hospitalized patients diagnosed with stroke

Indicator 8

Average length of stays: Average number of days waiting for transfer to an inpatient intensive functional rehabilitation unit (IFRU) from the time the patient is ready to begin rehabilitation until his or her admission/Average and median lengths of stay including emergency department (ED) and hospitalization/Average and median lengths of stay in intensive care/Average and median lengths of stay in stroke care unit (Determine ratio of number of days in stroke care unit compared with total number of days in hospital including stay in ED and not including stay in ED.)

Indicator 9

Proportion of acute stroke patients evaluated by a physiotherapist, occupational therapist, speech therapist, social worker, nutritionist, nurse or doctor (Proportion by type of health professional)

Numerator: Number of acute stroke patients evaluated by a physiotherapist, occupational therapist, speech therapist, social worker, nutritionist, nurse or doctor during hospitalization for acute stroke

Denominator: Total number of patients hospitalized for acute stroke

Indicator 10

Proportion of patients screened for dysphagia at admission and evaluated by a speech therapist, occupational therapist, nutritionist or other medically trained health professional

Numerator: Number of patients screened for dysphagia at admission and evaluated by a speech therapist, occupational therapist, nutritionist or other medically trained health professional

Denominator: Total number of patients screened for dysphagia at admission

Quality of care

Safety

Indicator 11

Proportion of post-stroke patients investigated for cardiac arrhythmia (electrocardiogram, heart monitor, telemetry, etc.)

Numerator: Number of post-stroke patients investigated for cardiac arrhythmia

Denominator: Total number of post-stroke patients

Indicator 12

Proportion of post-stroke patients screened for dysphagia within 4 hours following triage or within 24 hours following admission or prior to all oral intake of substances and liquids

Numerator 1: Number of post stroke patients screened for dysphagia within 4 hours following triage

Numerator 2: Number of post-stroke patients screened for dysphagia within 24 hours following admission

Numerator 3: Number of post-stroke patients screened for dysphagia prior to all oral intake of substances and liquids

Denominator: Total number of post-stroke patients

Indicator 13

Proportion of post-stroke patients evaluated for pressure sore risk and regularly evaluated to prevent these sores using a valid tool (Braden Scale)

Numerator: Number of post-stroke patients evaluated for pressure sore risk and regularly evaluated using a valid tool

Denominator: Total number of post-stroke patients

Indicator 14

Proportion of post-stroke patients neurologically evaluated using a valid scale (e.g., Canadian Neurological Scale [CNS], National Institutes of Health Stroke Scale [NIHSS])

Numerator: Number of post-stroke patients neurologically evaluated using a valid scale

Denominator: Total number of post-stroke patients

Indicator 15

Proportion of post-stroke patients screened or evaluated for risk of fall

Numerator: Number of post-stroke patients screened or evaluated for risk of fall

Denominator: Total number of post-stroke patients

Indicator 16

Proportion of post-stroke patients with complication of symptomatic intracranial hemorrhage following thrombolytic or endovascular therapy

Numerator: Number of post-stroke patients with complication of symptomatic intracranial hemorrhage following thrombolytic or endovascular therapy

Denominator: Total number of post-stroke patients given thrombolytic or endovascular therapy

Indicator 17

Proportion of post-stroke patients with one of the following complications during hospitalization: aspiration pneumonia, deep vein thrombosis, fever, pulmonary thromboembolism (PTE), shoulder subdislocation, urinary tract infection, contracture, malnourishment, depression/anxiety, gastrointestinal bleeding, convulsions (Result by type of complication)

Numerator: Number of post-stroke patients with one or more of these post-stroke complications during hospitalization

Denominator: Total number of post-stroke patients

Indicator 18

Proportion of patients given a carotid Doppler test within 24 hours

Numerator: Number of post-stroke patients given a carotid Doppler test within 24 hours

Denominator: Total number of post-stroke patients

Effectiveness

Indicator 19

Proportion of patients who die from stroke in hospital within 7 days and within 30 days following admission

Numerator 1: Number of patients who die from stroke within 7 days following admission to hospital

Numerator 2: Number of patients who die from stroke within 30 days following admission to hospital

Denominator: Total number of ischemic stroke patients hospitalized or discharged from hospital

Indicator 20

Proportion of patients with severe disability at discharge (mRS 0-3) (Calculate proportion of patients for each modified Rankin score, mRS of 1 to 5.)

Numerator: Number of patients with a modified Rankin score (mRS) between 0 and 3 at discharge

Denominator: Total number of patients with a modified Rankin score recorded at discharge

Indicator 21

Proportion of patients with increased shoulder pain based on pain intensity score evaluated with a valid tool using reference data during hospitalization

Numerator: Number of post-stroke patients with increased shoulder pain based on pain intensity score evaluated with a valid tool

Denominator: Number of post-stroke patients with shoulder pain

Indicator 22

Proportion of patients readmitted to short-term hospital care for a stroke-related issue after discharge (post 30 days)

Numerator: Number of patients readmitted to short-term hospital care for a stroke-related issue within 30 days after discharge

Denominator: Total number of post-stroke patients re-hospitalized after discharge

Continuity

Indicator 23

Proportion of post-stroke patients prescribed an anticoagulant, lipid-lowering medication, an antiplatelet, an antihypertensive, or a hypoglycemic at discharge (Result per medication)

Numerator: Number of post-stroke patients prescribed an anticoagulant, lipid-lowering medication, an antiplatelet, an antihypertensive, or a hypoglycemic at discharge

Denominator: Total number of post-stroke patients prescribed one or more medications

Indicator 24

Proportion of post-stroke patients with a record that includes a therapeutic nursing plan (TNP), an individualized intervention plan (IIP) or a care plan (CP)

Numerator: Number of post-stroke patients with a record that includes a therapeutic nursing plan (TNP), an individualized intervention plan (IIP) or a care plan (CP)

Denominator: Total number of post-stroke patients

Indicator 25

Transfer at discharge: Proportion of post-stroke patients transferred at discharge to inpatient rehabilitation, outpatient rehabilitation, return to residence, long-term care centre or palliative care (Result by patient's place of transfer)

Numerator: Number of post-stroke patients transferred to inpatient rehabilitation, outpatient rehabilitation, return to residence, long-term care center or palliative care

Denominator: Total number of post-stroke patients discharged from hospital

Indicator 26

Proportion of post-stroke patients referred at discharge to a secondary prevention program (Specify type of referral)

Numerator: Number of post-stroke patients referred at discharge to a secondary prevention program

Denominator: Total number of post-stroke patients discharged

Reactivity

Indicator 27

Proportion of post-stroke patients and caregivers met by the team to discuss management of the patient and his or her needs following discharge

Numerator: Number of post-stroke patients and caregivers met by the team to discuss management of the patient and his or her needs following discharge

Denominator: Total number of post-stroke patients discharged

Indicator 28

Proportion of post-stroke patients and caregivers instructed prior to discharge on the following stroke-related topics of interest: modifiable risk factors, warning signs and symptoms of stroke, how to activate medical emergency services, post-discharge services available, prescribed medications and community resources

Numerator: Number of post-stroke patients and caregivers instructed prior to discharge on these topics of interest

Denominator: Total number of post-stroke patients

Indicator 29

Proportion of post-stroke patients and caregivers who were invited to participate in advance planning of care or had a documented conversation with a health professional regarding resuscitation and level of care

Numerator: Number of post-stroke patients who were invited to participate in advance planning of care or had a documented conversation with a health professional regarding resuscitation and level of care

Denominator: Total number of post-stroke patients

APPENDIX 2

Detailed list of data to collect on patients' characteristics and clinical and organizational quality indicators

A. Data collection information	
A1. Date of collection DD/MM/YYYY ____ / ____ / ____	A2. Name. Collector: _____
A3. Patient ID 	
B. Sociodemographic characteristics	
B1. Center  1-Tertiary  2-Secondary  3-Primary	B3. Sex  1-Male  2-Female  3-Other: _____  99-Missing data
B2. Age at admission _____ years	
B4. Ethnicity  1-White  2-South Asian (e.g, Indian from India, Pakistani, SriLankan, Chinese)  3-Black  4-Filipino  5-Arab  6-Latin American  7-Southeast Asian (e.g., Vietnamese, Cambodian, Laotian, Thai)  8-Mideastern (e.g., Iranian, Afghan)  9-Other: _____	B5. Home region  1-Mauricie  2-Centre du Québec  3-Estrie  4-Montreal  5-Laval  6-Lanaudière  7-Montérégie  8-Other: _____  99-Missing data

 99-Missing data	
B6. Number of km between residence and hospital center: _____ km	
 99-Missing data	

C. Clinical characteristics		
C1. Stroke diagnosis  1-Left Sylvian  2-Right Sylvian  3-Other: _____  99-Missing data	C2. Administration of thrombolysis IV (alteplase)	
	 1-No	 2-Yes
	 3-Not applicable	 99-Missing data
	C3. Administration of thrombectomy	
 1-No	 2Yes	
 3-Not applicable	 99-Missing data	
C4. History of stroke  1-No  2-Yes  99-Missing data	C5. Other diagnoses <hr/> <hr/>	
	C6. Pre-stroke medications (relevant with ischemic stroke)	
	 1-Anticoagulant	 2-Antihypertensive
 4-Lipid-lowering medication	 5-Antiplatelet	 6-Other: <hr/>
 7-Other: _____	 8-Other: _____	 99-Missing data
C7. Covid-positive		
 1-No	 2-Yes	
 99-Missing data		

C8. First NIHSS evaluation (initial)  1-No  2-Yes  99-Missing data	C9. Initial NIHSS result: _____
C10. First modified Rankin assessment (initial mRS)  1-No  2-Yes  99-Missing data	C11. Initial mRS result: _____

D. Risk factors			
D1. Smoking  1-No  2-Yes  99-Missing data	D2. Physical inactivity  1-Yes  2-No  99-Missing data		
D3. Obesity  1-No  2-Yes  99-Missing data	D4. Poor nutrition  1-No  2-Yes  99-Missing data		
D5. Alcohol consumption  1-No  2-Yes  99-Missing data	D6. Drug use  1-No  2-Yes  99-Missing data		
D7. Arterial hypertension  1-No  2-Yes  99-Missing data	D8. Dyslipidemia  1-No  2-Yes  99-Missing data		
D9. Type 2 diabetes  1-No  2-Yes  99-Missing data	D10. Carotid stenosis  1-No  2-Yes  99-Missing data		
D11. Sleep apnea			

 1-No	 2-Yes	
 99-Missing data		

E. Patient flow / Time intervals				
E1. Date and time of arrival at triage		DD/MM/YYYY ____ / ____ / ____ HH: MIN ____ : ____		
E2. Date and time of admission to a short-term unit (regardless of unit) DD/MM/YYYY ____ / ____ / ____ HH : MIN ____ : ____				
E3. Admission to stroke care unit  1-No  2-Yes  3-Not applicable  99-Missing data				
E4. Date and time of admission to stroke care unit DD/MM/YYYY ____ / ____ / ____ HH: MIN ____ : ____				
E5. Admission to intensive care unit  1-No  2-Yes  3-Not applicable  99-Missing data				
E6. Date and time of admission to intensive care unit DD/MM/YYYY ____ / ____ / ____ HH: MIN ____ : ____				
E7. Presence of nursing evaluation note in the record  1-No  2-Yes  99-Missing data				
E8. Date and time of first nursing evaluation note DD/MM/YYYY ____ / ____ / ____ HH: MIN ____ : ____				
E9. Presence of physical therapy evaluation note in the record  1-No  2-Yes  99-Missing data				
E10. Date and time of first physical therapy evaluation note DD/MM/YYYY ____ / ____ / ____ HH: MIN ____ : ____				
E11. Presence of occupational therapy evaluation note in the record  1-No  2-Yes  99-Missing data				
E12. Date and time of first occupational evaluation note				

DD/MM/YYYY	____ / ____ / ____	HH: MIN	____ : ____
E13. Presence of speech therapy evaluation note in the record			
 1-No	 2-Yes	 99-Missing data	
E14. Date and time of first speech therapy evaluation			
DD/MM/YYYY	____ / ____ / ____	HH: MIN	____ : ____
E15. Presence of nutrition evaluation note in the record			
 1-No	 2-Yes	 99-Missing data	
E16. Date and time of first nutrition evaluation note			
DD/MM/YYYY	____ / ____ / ____	HH: MIN	____ : ____
E17. Presence of social worker evaluation note in the record			
 1-No	 2-Yes	 99-Missing data	
E18. Date and time of first social worker evaluation			
DD/MM/YYYY	____ / ____ / ____	HH: MIN	____ : ____
E19. Presence of doctor's evaluation note in the record			
 1-No	 2-Yes	 99-Missing data	
E20. Date and time of first doctor's evaluation			
DD/MM/YYYY	____ / ____ / ____	HH: MIN	____ : ____
E21. Documented discussion of levels of patient's care			
 1-No	 2-Yes	 99-Missing data	
E22. Dysphagia screening by a nurse or rehabilitation team member			
 1-No	 2-Yes	 99-Missing data	
E23. Date and time of dysphagia screening			
DD/MM/YYYY	____ / ____ / ____	HH: MIN	____ : ____
E24. Date and time of first oral administration			
DD/MM/YYYY	____ / ____ / ____	HH: MIN	____ : ____
E25. Presence of dysphagia			

 1-No	 2-Yes	 99-Missing data	
E26. Evaluation by a clinician in presence of dysphagia			
 1-No	 2-Yes	 3-Not applicable	
 99-Missing data			
E27. Referral to IFRU by a doctor			
 1-No	 2-Yes	 3-Not applicable	
 99-Missing data			
E28. Date and time of referral to IFRU			
DD/MM/YYYY	____ / ____ / ____	HH: MIN	____ : ____
E29. Admission to IFRU			
 1-No	 2-Yes	 3-Not applicable	
 99-Missing data			
E30. Date and time of admission to IFRU			
DD/MM/YYYY	____ / ____ / ____	HH: MIN	____ : ____
E31. CT carotid angiogram			
 1-No	 2-Yes	 3-Not applicable	
 99-Missing data			
E32. Date and time of CT carotid angiogram			
DD/MM/YYYY	____ / ____ / ____	HH: MIN	____ : ____

F. Evaluations

F1. Medical evaluation for cardiac arrhythmia			
 1-No	 2-Yes	 3-Not applicable	 99-Missing data
F2. Presence of cardiac arrhythmia			
 1-No	 2-Yes	 3-Not applicable	 99-Missing data
F3. Evaluation of pressure sore risk (Braden Scale) by the nurse			
 1-No	 2-Yes	 3-Not applicable	 99-Missing data

F4. Result of pressure sore evaluation (Braden Scale): _____

F5. Re-evaluation of pressure sore risk (Braden Scale) by the nurse

1-No 2-Yes 3-Not applicable 99-Missing data

F6. Evaluation of risk of fall by a nurse

1-No 2-Yes 3-Not applicable 99-Missing data

F7. Neurological evaluation by a nurse using the Canadian Neurological Scale

1-No 2-Yes 3-Not applicable 99-Missing data

F8. Result of neurological evaluation on the CNS: _____

F9. Neurological evaluation by the doctor using the NIHSS post revascularization treatment

1-No 2-Yes 3-Not applicable 99-Missing data

F10. Result of NIHSS post revascularization treatment: _____

